#### **4.3. Analysis Visit Window**

No analysis visit window is assigned. All data are summarized based on the visit name collected on the CRF page.

#### **4.4. Sample Size**

A minimum of 60 patients will be enrolled in the study. Patients will receive either 200 mg BID or 400 mg BID of SKI-O-703 or placebo in a 2:2:1 ratio.

Based on [Podolanczuk et al \(2009\)](#) at least 50% of patients in the active treatment group will be responders (R). A sample size of 24 patients per active treatment group and 12 patients in the placebo group will provide approximately 82.74% power to detect a difference between response rates of 50% and 1% in the active treatment and placebo groups, respectively, at the 2-sided 5% significance level. The test statistic used in the sample size calculation was the 2-sided Fisher's Exact test using the normal approximation method.

Patients that do not receive the study drug or do not provide at least 1 post baseline measurement will be excluded from the analysis above and replaced.

There will be no adjustment for multiple comparisons. The sample size calculation was performed using PASS 15 Power Analysis and Sample Size Software (2017). NCSS, LLC. Kaysville, Utah, USA, [ncss.com/software/pss](http://ncss.com/software/pss).

#### **4.5. Randomization, Stratification, and Blinding**

Patients will be randomly assigned in a 2:2:1 ratio to receive SKI-O-703 200 mg BID, SKI-O-703 400 mg BID, or matching placebo. A subset of at least 20 patients will be randomized to undergo PK/PL assessments at a selected number of sites. An interactive voice response system (IVRS) will be used to administer the randomization schedule. The randomization schedule will be generated using SAS software Version 9.4 or later (SAS Institute Inc., Cary, North Carolina) for IVRS, which will link sequential patients randomization numbers to treatment codes. The randomization will be stratified by prior TPO-receptor agonist use (yes/no) and degree of baseline thrombocytopenia (ie, baseline platelet count < or  $\geq$ 15,000/ $\mu$ L). It will also use an appropriate block size, which will not be revealed.

Patients who are randomly assigned and not dosed will be replaced. Patients who discontinue the study for any reason after dosing will not be replaced.

This is a double-blind study. Neither the patients nor the investigator/site personnel will be aware of the treatment assignment for the patients in each cohort. Additionally, the study drugs will be identical in number and appearance for each cohort. Blinding will be

maintained throughout the study by use of active or placebo dosage forms of similar appearance.

The DMC will receive first 1-week safety and PK unblinded data by treatment group or unblinded (if necessary) confidential reports of the first 5 patients enrolled in the safety run-in period from an independent statistician for review, which has to be handled strictly confidentially. None of these reports can be delivered to unauthorized persons.

#### **4.6. Analysis Set**

##### **4.6.1. Safety set**

The Safety set will consist of all patients who receive at least 1 dose of study drug (SKI-O-703 or placebo). Patients will be analyzed according to the treatment they received. This analysis set will be used in the analysis of demographic and safety data.

##### **4.6.2. Intent-to-Treat (ITT) set**

The ITT set will consist of all randomized patients who receive at least 1 dose of study drug (SKI-O-703 or placebo) and have at least 1 post-baseline platelet assessments. Patients will be analyzed according to the treatment arm to which they were randomized. This analysis set will be used for efficacy summaries, including the analysis of the primary endpoint.

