4.2.3 Replacements

Subjects who are randomly assigned and not dosed will be replaced. Subjects who discontinue the study for any reason after dosing will not be replaced.

5 Study drugs

Two dose levels of SKI-O-703 will be evaluated: 200 mg BID and 400 mg BID. The SKI-O-703 capsules will contain 100 mg of drug substance. Placebo capsules are filled with microcrystalline cellulose.

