7.4 Sample Size Calculations

A minimum of 60 subjects will be enrolled in the study. Subjects will receive either 200 mg BID or 400 mg BID of SKI-O-703 or placebo in a 2:2:1 ratio.

Based on [Podolanczuk et al \(2009\)](#) at least 50% of subjects in the active treatment group will be responders (R). A sample size of 24 subjects per active treatment group and 12 subjects in the placebo group will provide approximately 82.7% power to detect a difference between response rates of 50% and 1% in the active treatment and placebo groups, respectively, at the 2-sided 5% significance level. The test statistic used in the sample size calculation was the 2-sided Fisher's Exact test using the normal approximation method.

Subjects that do not receive the study drug or do not provide at least 1 post baseline measurement will be excluded from the analysis above and replaced.

There will be no adjustment for multiple comparisons. The sample size calculation was performed using PASS 15 Power Analysis and Sample Size Software (2017). NCSS, LLC. Kaysville, Utah, USA, ncss.com/software/pass.

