## 5. Patient Disposition

### 5.1. Disposition

The number of patients screened, the number and percentage of patients who failed screening, and the violated eligibility criteria will be summarized. The above percentages will be based on the number of patients screened.

A summary of the analysis sets includes the number and percentage of patients for the following categories: Safety set, ITT set, and PP set. The above percentages will be based on the number of patients randomized.

Patient disposition will be summarized for the ITT set. A disposition of patients includes the number and percentage of patients who completed study treatment, discontinued study treatment, completed the study, and discontinued from the study. The reasons for study discontinuation, the reasons for study treatment discontinuation will also be summarized in this table, as collected on eCRF pages.

The number and percentage of patients by region, study site and treatment group will be tabulated based on all randomized patients.

Patient disposition data will be presented in listings.

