#### 8.1.1. Primary Analysis

The platelet responses after using rescue medication during treatment period will be set to missing and will be imputed as the average of the last 2 previous non-missing platelet counts. For example, if platelet count in Week 2 Day 8, Week 3 and Week 5 are 45,000, missing, and 48,000 respectively, the average will be calculated by results from Week 2 Day 8 and Week 5.

The primary efficacy endpoint will be summarized as overall platelet response rate (ORR) with exact unconditional 95% confidence intervals (CI) by treatment group. The ORR difference and exact unconditional 95% CI will be provided between each of active treatment groups and placebo group, and between two active treatment groups. The p-value from Fisher's exact test will be presented.

For patients whose ORR cannot be adequately determined, their ORR will be imputed using a non-responder imputation (NRI) approach.

Summary statistics will be provided on the number (%) of patients achieving platelet response by each treatment and the combined active treatment groups. The differences in the ORR, 95% CI and p-value from a Fisher's exact test will therefore be provided for:

- Each active treatment group (200 mg BID, 400 mg BID) vs. placebo
- Combine active treatment groups vs. placebo
- 200 mg BID vs. 400 mg BID.

A logistic regression model will also be performed on platelet response as dependent variable and treatment group, baseline platelet count and prior TPO-receptor agonist use as covariates. The odds ratio for the treatment effect compared to placebo (together with 95% CI and p-value) will be provided.

Bar plots on difference in proportions of ORR and exact unconditional 95% CI will be provided by treatment group and combined active treatment group.

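### The set labelled ITT is a modified ITT set that drops dosed patients with no post-baseline platelet count before non-responder imputation can reach them, and the rules on replacing such patients conflict

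*SAP*

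**What the plan says.** **Analysis set.** SAP 4.6.2 and Protocol 7.5 define the ITT set in the same way: patients must be randomised, have received at least one dose, and "have at least 1 post-baseline platelet assessments". Both sections assign the primary endpoint to this set.

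**Undetermined response.** SAP 8.1.1 says that where response cannot be adequately determined, "their ORR will be imputed using a non-responder imputation (NRI) approach".

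**Replacement, first rule.** Protocol 7.4 says that subjects who are not dosed, or who "do not provide at least 1 post baseline measurement will be excluded from the analysis above and replaced". The Sample Size entry of the protocol synopsis and SAP 4.4 carry the same sentence.

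**Replacement, second rule.** Protocol 4.2.3 replaces subjects who were randomised but not dosed, and adds: "Subjects who discontinue the study for any reason after dosing will not be replaced". SAP 4.5 repeats this for patients.

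**Disposition.** SAP 5.1 states: "Patient disposition will be summarized for the ITT set". Protocol 7.7.1 describes a broader summary that includes subjects who enrolled, were randomly assigned, discontinued and completed.

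**The concern.** Membership of the primary set depends on something that happens after randomisation and dosing. A patient who takes study drug and never has another platelet count is the plainest case of a response that cannot be determined. The plan scores such a patient as a failure if any later count exists, however late, and leaves the patient out entirely if none exists.

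If early loss differs between arms, the denominators shrink unequally. With 24 patients per active arm and 12 on placebo, one or two patients can matter.

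The replacement conflict is a separate, operational problem. The people running the IVRS cannot tell whether to replace a dosed patient who leaves before the first count, so both total enrolment and the planned 24/24/12 depend on which section they read.

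Because the SAP disposition table uses the same set, it would leave out the earliest discontinuations and their reasons.

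**Working it through.** **1. The plan's own power figure.** Inputs from SAP 4.4: "A sample size of 24 patients per active treatment group and 12 patients in the placebo group"; response rates of 50% and 1%; testing "at the 2-sided 5% significance level"; and "approximately 82.74% power to detect a difference" (82.7% in Protocol 7.4). The method is Fisher's exact test by normal approximation. I used the continuity-corrected form with pooled variance under the null:

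Power = Φ{[(p1 − p2) − ½(1/n1 + 1/n2) − 1.96·SE0] / SE1}

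- p1 − p2 = 0.50 − 0.01 = 0.49
- Correction = ½(1/24 + 1/12) = 0.0625
- Pooled rate = (24×0.50 + 12×0.01)/36 = 0.3367
- SE0 = √[0.3367×0.6633×(1/24 + 1/12)] = 0.1671
- SE1 = √[0.50×0.50/24 + 0.01×0.99/12] = 0.1060
- Power = Φ[(0.49 − 0.0625 − 0.3275)/0.1060] = Φ(0.943) = 82.73%

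This reproduces the stated figure, so the arithmetic is not at fault.

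**2. One patient traced through the text.** Take a patient dosed on Day 1 who leaves the study before any further blood draw.

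- SAP 4.6.2 and Protocol 7.5: not in the ITT set.
- SAP 8 runs efficacy in the ITT set and repeats it in the per-protocol set, which SAP 4.6.3 makes a subset of ITT. The patient is in neither.
- SAP 8.1.2: both sensitivity analyses repeat the primary analysis, and neither names a wider set. The treatment-policy analysis ignores rescue use and discontinuation but does not readmit this patient.
- SAP 8.1.1 non-responder rule: never reached.
- Protocol 7.4 and SAP 4.4: replaced. Protocol 4.2.3 and SAP 4.5: not replaced. No section says which prevails.
- SAP 5.1: missing from the disposition summary, though the count of randomised patients outside the ITT set can be recovered from the analysis-set table.

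**3. Effect on the primary test.** The documents give no rate of dosed patients without a count, so the numbers of exclusions below are assumptions. Each excluded patient is a non-responder if kept. P-values are two-sided Fisher's exact.

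| Assumed exclusions | Kept as non-responder | Dropped |
|---|---|---|
| 2 active | 7/24 vs 0/12, p=0.070 | 7/22 vs 0/12, p=0.036 |
| 1 active | 7/24 vs 0/12, p=0.070 | 7/23 vs 0/12, p=0.0695 |
| 1 placebo | 11/24 vs 1/12, p=0.031 | 11/24 vs 1/11, p=0.055 |
| 2 active, design-like result | 12/24 vs 0/12, p=0.0025 | 12/22 vs 0/12, p=0.0018 |
| 1 placebo, design-like result | 12/24 vs 0/12, p=0.0025 | 12/24 vs 0/11, p=0.0055 |

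In the fourth row the active response rate rises from 12/24 = 50% to 12/22 = 54.5%.

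If the remaining patients respond at 50% and 1%, the probability that dropping rather than keeping changes significance is about 0.001% for one active exclusion, 3.6% for two active and 1.6% for one placebo.

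**4. Effect on power, by the method in step 1.** Let d be the assumed fraction of dosed patients without a count, equal in all arms.

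- Kept as non-responders, both rates multiplied by (1 − d): 82.7% at d=0, 77.5% at d=5%, 71.6% at d=10%. Full enumeration of Fisher's test gives 93.9%, 91.1% and 87.4%.
- Dropped and not replaced: 81.7% with 23/12, 80.7% with 22/12, 78.6% with 24/11, 76.4% with 22/11.
- Dropped and replaced: 24/12 and 82.7% are retained, but the second replacement rule is broken.

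**The case against.** The strongest reply is that very few patients can fall into this gap. Hematology is scheduled for everyone on Day 4 (±1 day), again on Day 8, at the early-withdrawal visit and at Week 16. Protocol 1.4 gives those who stop treatment an end-of-treatment visit and follow-up for the intended duration, and Protocol 4.2.2 asks for end-of-study assessments whenever possible. The ITT definition asks for any post-baseline count, not one on treatment. A patient who stops early for intolerance and attends any later blood draw therefore stays in the denominator. This stands, and it limits the size of the problem.

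Four stronger readings are tempting, and the documents do not support them.

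- *The ITT definition contradicts non-responder imputation.* It does not. SAP 8 confines efficacy to the ITT set and the imputation operates within it for patients with partial data, so both rules can be executed. What remains is that they treat the same condition in opposite ways.
- *Replacement breaks the randomised comparison.* Replacements would be randomised through the IVRS in a double-blind trial with a minimum, not a fixed, enrolment of 60. Any bias comes from the exclusion.
- *The exclusion favours the drug.* It can, but the placebo example moves away from significance.
- *No one is ever replaced after dosing.* Protocol 4.2.3 and SAP 4.5 cover those who discontinue the study. A dosed patient who stays but never has a count falls outside that sentence.

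On disposition, the exclusions are not hidden altogether. SAP 5.1 also reports the Safety, ITT and per-protocol sets against all randomised patients and lists disposition data, and SAP 9.1 tabulates adverse events leading to drug withdrawal on the Safety set. The ITT-based summary still omits these patients and their reasons.

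**Conclusion.** The point holds in a limited form. The primary set is a modified ITT set under an ITT label, and no planned efficacy analysis could show whether its exclusion mattered. The replacement rules conflict outright, in both documents, for a dosed patient who discontinues before any post-baseline count.

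The numerical effect is probably small. It rests on an exclusion count that the documents do not supply, and the crossings of 0.05 shown are chosen illustrations: the active one needs two exclusions and a response rate of 29% (7/24), well below the planned 50%. Results at the design rates stay significant under either rule. This should be corrected because it is ambiguous and cheap to repair; it does not invalidate the planned comparison.

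**What to change.** 1. In Protocol 7.5 and SAP 4.6.2, define the primary efficacy set as all randomised patients who received at least one dose, analysed as randomised, with no post-baseline count scored as non-response. Membership still depends on dosing, but under the blind and with the first dose given at the site on Day 1 this is a much weaker dependence.
2. Keep the current set for a sensitivity analysis, named modified ITT.
3. In the synopsis Sample Size entry, Protocol 7.4 and SAP 4.4, delete the post-baseline-measurement condition from the exclude-and-replace sentence, leaving only undosed patients. This agrees with Protocol 4.2.3 and SAP 4.5.
4. In SAP 5.1, report disposition and reasons for discontinuation on all randomised patients.

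The cost is wording in both documents, with no new visits or data. The reported response rate may be slightly lower, and if patients without counts were as common as 5% in every arm, power by the plan's method would be 77.5% instead of 82.7%.

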##### **4.6.3. Per-protocol (PP) set**

The PP set will consist of all patients in ITT set with no major protocol violations that may impact the analysis. Major protocol violations will be identified during the study according to the protocol deviation list and treatment compliance defined in [Section 7.4.2](#). Patients will be analyzed according to the treatment arm to which they were randomized. This analysis set will be used for efficacy summaries, including the analysis of the primary endpoint.

##### **4.6.4. Pharmacokinetic (PK) set**

The PK set will consist of all patients who receive SKI-O-703 and have at least 1 measurable plasma concentration. Patients who have partial data and/or major protocol deviations that may impact PK, and patients who experience emesis, will be evaluated on a case-by-case basis and may be excluded from the PK analysis set. This analysis set will be used for summaries of PK data.

##### **4.6.5. Pharmacodynamic (PD) set**

The PD set will consist of all patients who receive at least 1 dose of study drug (SKI-O-703 or placebo) and have at least 1 evaluable postdose PD value. Patients who have partial data and/or major protocol deviations that may impact PD will be evaluated on a case-by-case basis and may be excluded from the PD analysis set. This analysis set will be used for summaries of PD data.

#### **4.6.6. Pharmacokinetic (PK)/pharmacodynamic (PD) set**

All patients included in the PK and PD analysis sets. This analysis set will be used for the PK/PD analyses.

#### **4.7. Imputation of Missing Date**

##### Incomplete Start and Stop Date of Concomitant Medications and Adverse Events:

For the purpose of inclusion in prior and/or concomitant medication tables and treatment-emergent adverse events (TEAE), incomplete medication/AE start and stop dates will be imputed as follows:

Missing start dates (where UK, UKN and UNKN indicate unknown or missing day, month and year respectively):

- UK-MMM-YYYY: If the month and year are different from the month and year of the first dose of study drug, assume 01-MMM-YYY. If the month and year are the same as the first dose of study drug month and year and the end date (after any imputation) is on or after the first dose of study drug, then assume the date of the first dose of study drug. If the month and year are the same as the first dose of study drug month and year and the end date (after any imputation) is prior to the first dose of study drug, then assume the end date for the start date;
- DD-UKN-YYYY/UK-UKN-YYYY: If the year is different from the year of the first dose of study drug, assume 01-JAN-YYYY of the collected year. If the year is the same as the first dose of study drug year and the end date (after any imputation) is on or after the first dose of study drug, then assume the date of the first dose of study drug. If the year is the same as the first dose of study drug and the end date (after any imputation) is prior to the first dose of study drug, then assume the end date for the start date.

Missing stop dates (where UK, UKN and UNKN indicate unknown or missing day, month and year respectively):

- UK-MMM-YYYY: Assume the last day of the month;
- DD-UKN-YYYY/UK-UKN-YYYY: Assume 31-DEC-YYYY.

If start date is completely missing and end date is not prior to the first dose, then the medication will be classified as both prior and concomitant. If the start date is completely missing and the end date is prior to the first dose of study drug, then the medication will be classified as prior. If the end date is missing, then the medication will be classified as ongoing. Medications for which the start and end dates are missing will be classified as prior and concomitant.

If start date is completely missing and end date is not prior to the first dose, then the AE will be classified as TEAE. AEs for which the start and end dates are missing will be classified as TEAEs.

## 5. Patient Disposition

### 5.1. Disposition

The number of patients screened, the number and percentage of patients who failed screening, and the violated eligibility criteria will be summarized. The above percentages will be based on the number of patients screened.

A summary of the analysis sets includes the number and percentage of patients for the following categories: Safety set, ITT set, and PP set. The above percentages will be based on the number of patients randomized.

Patient disposition will be summarized for the ITT set. A disposition of patients includes the number and percentage of patients who completed study treatment, discontinued study treatment, completed the study, and discontinued from the study. The reasons for study discontinuation, the reasons for study treatment discontinuation will also be summarized in this table, as collected on eCRF pages.

The number and percentage of patients by region, study site and treatment group will be tabulated based on all randomized patients.

Patient disposition data will be presented in listings.

### 5.2. Protocol Deviations

The protocol deviations/violations will be identified and assessed by clinical research physician or designee following institution standard operational procedures. The protocol deviations/violations will be summarized for all randomized patients by treatment group and overall based on all randomized patients.

A listing of patients with protocol deviations/violations will be provided with detail protocol deviation category and description presented.

## 6. Demographics and Baseline Characteristics

The demographics and baseline characteristics will be summarized by treatment group based on ITT set, unless otherwise specified. The patient data will also be presented in listings.

### 6.1. Demographics

The following demographics and baseline characteristics will be summarized based on ITT set, and repeated on Safety set:

- Age (years)

- Sex (Male, Female)
- Race (White, Black or African American, Asian, American Indian or Alaska Native, Native Hawaiian or Other Pacific Islander, Other)
- Ethnicity (Hispanic or Latino, Not Hispanic or Latino)
- Height (cm)
- Weight (kg)
- Body mass index (BMI) (kg/m^2)

Body mass index is calculated as (body weight in kilograms) / (height in meters). A patient's age in years is calculated using the date of the informed consent and date of birth.

Patient demographic and baseline characteristics will be presented in a listing.

## **6.2. Baseline Disease Characteristics**

The following disease characteristics will be summarized.

- Number of previous lines of therapy
- Number of previous lines of therapy categories (0-2 vs.  $\geq 3$ )
- Response to previous treatment (non-responders vs. relapsed)
- Previous splenectomy (yes vs. no)
- Baseline platelet count
- Baseline platelet count categories (<15,000/ $\mu$ L vs. 15,000/ $\mu$ L-30,000/ $\mu$ L)
- TPO-receptor agonist use (yes vs. no)

Patient baseline and disease characteristics will be presented in a listing.

